### **3.3 Procedures for Handling Missing Data**

The primary analysis will be based on the observed data where average weekly SBMs and CSBMs will be standardized to 7-day frequencies. This amounts to missing days during the week being imputed with the mean for the non-missing days. A valid week will require at least 4 non-missing diary days. Hence, for the primary analysis, weeks with less than 4 diary days are treated as a non-responder for that week. To further assess the impact of missing weeks on the efficacy analyses, a sensitivity analysis will be carried out by treating weeks with less than 4 diary days as a responder for that week.

The valid week rule will also apply for stool consistency and straining score although it is assumed that if the diary was filled out for frequency of stools, it would also be filled out with respect to these items. However, the average weekly stool consistency and the average weekly straining score will be calculated on the observed number of responses without any standardization. For the purposes of calculating an average, days with no stools reported (i.e., a 0 was recorded for the answer to IVRS question) will be scored as 0 for average weekly stool consistency and average weekly straining score.

An endpoint week will be defined as the last valid week during the first 12-weeks of the treatment period and the last valid week of the 26-week treatment period where each weekly

efficacy variable was obtained. This amounts to creating an endpoint last observation carried forward such that each subject's endpoint value represents the last experience while receiving study drug during the first 12-weeks and the total 26-week treatment period. In the few cases where no efficacy data is collected during the 12-week treatment period, the endpoint week will be considered a non-response or missing if no frequency or stool consistency data are obtained.

Otherwise, all other observed data will be used in the analyses.

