The week during which the day of the last dose occurs will be considered the last valid week during the 26-week treatment period, assuming it contains at least 4 valid daily IVRS diary days. Otherwise, the last valid week will be the preceding week. The last valid week during the treatment period will be used as the endpoint week for weekly efficacy summaries. If the last valid week is before week 12, the week 12 endpoint and week 26 endpoint will use this week. If the last valid week is after week 12, the week 12 endpoint will use week 12 and week 26 endpoint will use the last valid week obtained after week 12.

Only data captured from the first dose until the last dose will be used to derive the weeks during the 26-week treatment period,

All data listings will contain a relative study day, regardless of whether the data was collected via IVRS diary or eCRF.

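### The SAP 3.5 endpoint-week rule can select a week that SAP 3.3 does not count as valid; only descriptive, secondary endpoint-week results are affected

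*SAP*

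**What the plan says.** SAP 3.3 sets the validity standard: "A valid week will require at least 4 non-missing diary days". It then defines the endpoint: "An endpoint week will be defined as the last valid week during the first 12-weeks of the treatment period", with a matching definition for the full 26 weeks, applied wherever the particular weekly variable was obtained. It states the purpose: "This amounts to creating an endpoint last observation carried forward". SAP 2.3.1 repeats the last-valid-week definition for nearly every weekly variable, and notes that different abdominal symptoms may end up with different endpoint weeks.

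SAP 3.5 describes a procedure instead of a definition:

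- Start from the last dose: "The week during which the day of the last dose occurs will be considered the last valid week during the 26-week treatment period", provided that week has at least 4 diary days.
- If it does not: "Otherwise, the last valid week will be the preceding week".
- Early stoppers: "If the last valid week is before week 12, the week 12 endpoint and week 26 endpoint will use this week".
- Everyone else: "If the last valid week is after week 12, the week 12 endpoint will use week 12", with the later week serving as the Week 26 endpoint.

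Protocol 10.4 and 10.6 contain the same pair of rules, so the protocol does not settle which governs.

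**The concern.** The SAP 3.5 procedure applies the 4-day test once, to the last-dose week. Neither the week before it nor Week 12 is tested, and nothing checks that the selected week holds the variable being analysed. The step-back also stops after one week, whereas a carried-forward value requires searching back until a valid week is found. Two programmers, one following 3.3 and one following 3.5, could therefore assign different endpoint weeks to the same subject and produce different Week 12 and Week 26 endpoint tables. The subjects concerned are those with sparse diaries, some of them near discontinuation, which is where a last-on-drug summary is meant to be informative.

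**Working it through.** **Inputs.** Valid week: at least 4 diary days (SAP 3.3). Week windows: protocol 10.6 and SAP 3.5. On-drug data only: SAP 3.5. There is no stated figure to reproduce, so I applied both rules literally to constructed diaries. Diaries are complete up to the last dose except where noted. Results are shown as (Week 12 endpoint, Week 26 endpoint).

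| Case | SAP 3.3 | SAP 3.5 | Diary days in the disputed week |
|---|---|---|---|
| A. Last dose Day 182; 3 diary days in Week 12 | (11, 26) | (12, 26) | Week 12: 3 |
| B. Last dose Day 100; 2 diary days in Week 14 | (12, 13) | (12, 14) | Week 14: 2 |
| C. Last dose Day 72; 3 diary days in Week 10 | (9, 9) | (10, 10) | Week 10: 3 |
| D. Last dose Day 84; Week 12 complete | (12, 12) | (12, 12) | none |

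In B, Week 15 runs from Day 99, so it holds 2 on-drug days and fails. In C, Week 11 runs from Day 71 in the protocol and also holds 2. The SAP prints Day 70 as its start, which would make 3 and change nothing. In D, neither the before-Week-12 nor the after-Week-12 sentence applies, but the general SAP 3.5 sentence that the last valid week is the endpoint week gives Week 12. A to C show the two failure paths: an untested Week 12 (A) and an untested preceding week (B, C).

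**What the subject receives.** SAP 3.3 scores a week with fewer than 4 days as non-response, so a responder variable defaults to non-response. SAP 2.3.1 and 3.3 require a valid week for CSBM, SBM, pain, other abdominal symptom, stool consistency and straining averages, so a continuous variable normally becomes missing. A value from fewer than 4 days arises only if the programmer takes the 3.5 label of last valid week as sufficient. None of these is the carried-forward value of 3.3.

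**Once-weekly ratings.** IBS severity, constipation severity, adequate relief and degree of relief are recorded once a week. If the last-dose week has 4 or more diary days but no rating, SAP 3.5 still selects it and the value is missing. SAP 2.3.1 and 3.3 would use the last week with a rating.

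**Frequency, by assumption.** The documents give no completion rate. Let each day be completed independently with probability c. Then P(week invalid) = sum over k = 0 to 3 of C(7,k) c^k (1-c)^(7-k).

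- c = 0.90: 0.0025515 + 0.0001701 + 0.0000063 + 0.0000001 = 0.0027, or 0.3%.
- c = 0.80: 0.0286720 + 0.0043008 + 0.0003584 + 0.0000128 = 0.0333, or 3.3%.
- Wider range: 0.02% at 0.95, 12.6% at 0.70, 29.0% at 0.60.

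If all 600 subjects continued past Week 12, the Week 12 path would affect 600 × 0.0027 = 1.6 subjects at 90% and 600 × 0.0333 = 20 at 80%. Letting completion vary between subjects (beta-distributed, mean 80% to 90%, concentration 3 to 50) and keeping only those meeting the 11-of-14-day screening requirement gives 0.5% to 3.4%.

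For early stoppers, suppose the last-dose day is uniform within its week. With complete diaries, 3/7 = 43% have fewer than 4 on-drug days in that week and reach the untested step; the share is 49% at c = 0.90 and 57% at c = 0.80. The preceding week must then also be invalid: 0.49 × 0.0027 = 0.13% and 0.57 × 0.0333 = 1.9% of early stoppers.

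**The case against.** The strongest reply is that SAP 3.5 is shorthand in a visit-windows section. The last-valid-week definition is stated in 3.3 and repeated throughout 2.3.1, valid-week rules elsewhere block most values from sparse weeks, and SAP 4 says programming specifications will be finalized before database lock. Much of this stands. It limits the usual error to a missing value or a default non-response, and it means the conflict can still be settled in time. It does not remove the conflict: applying the 4-day rule after 3.5 has chosen the week does not retrieve the earlier valid week that 3.3 carries forward.

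Three stronger readings are tempting, and the documents do not support them.

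- A reader might infer that a subject who stops in Week 1 with fewer than 4 diary days is given a screening week, and so a baseline value. SAP 3.5 confines the endpoint to the treatment period and adds "Only data captured from the first dose until the last dose will be used to derive the weeks". No baseline value can enter. Such a subject has no valid week, so the outcome is non-response or missing. The SAP 3.3 sentence on subjects without efficacy data literally covers only those with none at all, so this is worth stating, but it is a small gap.
- A reader might infer that a last valid week equal to Week 12 is left undefined. The general sentence in SAP 3.5 covers it (case D).
- A reader might infer that the confirmatory results are exposed. The primary and the eight key secondary variables count weekly responses over 12 or 26 weeks and never use the endpoint week.

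**Conclusion.** The concern holds in limited form. As written, SAP 3.5 and protocol 10.6 can select an invalid week, or a week without the variable, in conflict with SAP 3.3 and 2.3.1. The two rules agree when Week 12 and the last-dose week, or the week before it, are valid and hold the variable, so only subjects with sparse diaries or a missing weekly rating are affected. The reach is the Week 12 and Week 26 endpoint-week summaries and tests of secondary weekly variables, whose p-values SAP 3.6 calls descriptive. No confirmatory conclusion can change.

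The likely number is small: roughly 0.3% to 3.3% of subjects continuing past Week 12 for the Week 12 path, and a smaller share of early stoppers for the preceding-week path. These figures assume independent diary days and 80% to 90% completion, neither of which comes from the documents. Diaries that thin out before discontinuation would raise the early-stopper share. This is a minor correction, worth making because it is cheap and because the tables should not depend on which section a programmer reads.

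**What to change.** Replace the endpoint-week paragraph of SAP 3.5 with the 3.3 definition, applied separately to each variable:

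- The Week 12 endpoint is the latest of Weeks 1 to 12 on study drug that is valid for that variable. The Week 26 endpoint is the latest such week of Weeks 1 to 26.
- Valid means at least 4 diary days for items collected daily, and a recorded rating for items collected once a week.
- If no such week exists, the endpoint is non-response for a binary variable and missing for a continuous one.

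The rule has to be per variable. Choosing one week per subject from diary-day counts alone would conflict with SAP 2.3.1 and would lose once-weekly ratings recorded in an earlier week. Applied to cases A to D, the rule gives (11, 26), (12, 13), (9, 9) and (12, 12), and no selected week has fewer than 4 days.

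The cost is one paragraph of SAP text, carried into the programming specifications before database lock and unblinding. Protocol 10 allows changes to its statistical section to be made in the SAP, so no protocol amendment is needed. No primary or key secondary analysis changes.

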### **3.6 Statistical Analyses**

Summary tabulations will be presented that will display descriptive statistics for each treatment group. The number of observations, mean, standard deviation, minimum, median, and maximum values will be displayed for continuous variables, and the number and percent of subjects per category will be displayed for categorical data. For subject disposition,

demographic and baseline characteristics, medical history, gastrointestinal disease history, and prior medications, an overall column (i.e., all subjects combined) will be included.

Statistical analyses will be performed at the two-sided significance level of 0.050 according to the testing procedure described below. The testing procedure will preserve the experiment wise Type I error rate at 5%. All secondary p-values will be considered descriptive.

### **3.6.1 Subject Disposition**

Subject disposition information will be summarized by treatment group and overall. The number and percent of subjects who are randomized, who took a dose of study drug, who complete the study, and who withdraw early from the study will be presented. The primary reason for early withdrawal will also be tabulated. The number of subjects randomized will be used as the denominator for the percentage calculation. Subject disposition, inclusion / exclusion criteria, and protocol deviations will be listed.

The number and percent of subjects in each analysis set will also be tabulated.

### **3.6.2 Demographic and Background Characteristics**

The treatment groups will be descriptively assessed for comparability of demographic and baseline characteristics. Variables included in this assessment will be the demographic characteristics of age at informed consent (years), gender, race, ethnicity, body weight (kg), and BMI (kg/m^2). These variables will be summarized for each treatment group and overall. Screening values (week -1, week -2) and baseline values (average of week -1 and week -2) for average weekly CSBMs, average weekly SBMs, average weekly stool consistency, average weekly straining score, and average weekly abdominal symptoms of pain, discomfort, bloating, fullness, and cramping will also be summarized for each treatment group.

Weekly ratings of IBS severity and constipation severity will also be summarized for each of the 2 weeks of the screening period. Both categorical and continuous descriptive statistics will be used for the weekly ratings.

Medical history and gastrointestinal (GI) history will be summarized for the number and percentage of subjects for each body system by treatment group and overall. Medical history includes verbatim terms recorded for the subjects. GI history includes duration (years) since IBS symptoms began before randomization, duration (months) since last colonoscopy before randomization, and whether colonoscopy findings are not significant. A summary table will be presented for each analysis set. Medical and GI history will also be listed.

### **3.6.3 Prior/Concomitant Medication**

All prior and concomitant medications administered during the study will be coded using the latest available version of the World Health Organization (WHO) Drug Reference List. Prior medications include medications that were started and stopped prior to the first dose of study drug. Concomitant medications include medications that started any time and were taken at any time after the first dose of study drug until the end of the treatment period. Medications

missing both start and stop dates or having a start date prior to the start of study drug and missing stop date will be counted as concomitant.

The number and percentage of subjects taking prior and concomitant medications will be summarized by Anatomical Therapeutic Chemical (ATC) class and preferred name by treatment group. Prior medications will also be summarized overall. If a subject took a particular coded medication more than once, the subject will be counted once for that coded medication total. If a subject had more than one coded medication in a therapeutic class, the subject will be counted only once in that therapeutic class total. Summary tables will be presented for each of the analysis sets. Prior medications will be summarized separately from concomitant medications.

A listing of all medications including the reported term, preferred name, ATC class, start and stop dates, and other relevant data will be provided.

### **3.6.4 Study Drug Exposure and Compliance**

Days of exposure to randomized study drug will be summarized with descriptive statistics by treatment group for each of the analysis sets. In addition, a contingency table will be provided to display the number and percentage of subjects in each treatment group with exposure in the following categories:  $\leq 2$  weeks,  $>2$  to  $\leq 4$  weeks,  $>4$  to  $\leq 8$  weeks,  $>8$  to  $\leq 12$  weeks,  $>12$  to  $\leq 16$  weeks,  $>16$  to  $\leq 20$  weeks, and  $>20$  to  $\leq 26$  weeks.

Days of possible exposure is defined as:

$$\text{date of last dose of study drug} - \text{date of first dose of study drug} + 1.$$

When the last known dose date is missing, the last known clinic visit date during the treatment period will be used, and the plus 1 will be removed from the calculation.

The percent compliance to study drug will be calculated as the total number of tablets dispensed minus the total number of tablets returned divided by two times the number of days during the treatment period, then multiplied by 100.

Summary statistics will be presented for percent compliance to study drug by treatment group. The count and percentage of subjects with overall compliance  $<80\%$ ,  $80\%$ - $100\%$ ,  $100\%$ - $120\%$  and  $>120\%$  will also be tabulated by treatment group.

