6.2. Packaging, Storage, and Labeling

The study drug will be supplied in white square HDPE bottles with child resistant polypropylene (CRC) closures with an induction seal plus desiccants. Each bottle will contain sixty-six (66) tablets.

Tenapanor and placebo tablets should be stored in the original packaging between 2°C and 30°C. Temperature excursions are allowed from -30°C to 50°C for a maximum of 1 week.

Each bottle will be labeled with a single panel, double blind label.

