### **2.2.1 Treatments Administered**

Study drug will be dispensed only to eligible subjects under the supervision of the Investigator or identified sub-Investigator(s). Eligible subjects will be randomized 1:1 into one of two treatment groups: tenapanor 50 mg BID or placebo BID. Subjects will take one

tenapanor tablet or one matching placebo tablet twice daily, immediately prior to breakfast or the first meal of the day and immediately prior to dinner.

Subjects will receive one bottle of drug at Visit 2 (Day 1), Visit 4 (Day  $29 \pm 3$ ), Visit 5 (Day  $57 \pm 3$  days), Visit 6 (Day  $85 \pm 3$  days), and Visit 7 (Day  $113 \pm 3$  days), and two bottles of drug at Visit 8 (Day  $141 \pm 3$  days). At each visit the subject will be asked to return their unused drug and bottles. All unused study drug and bottles should be returned to the study site. Study drug compliance will be monitored closely by the clinical site staff and will be verified by the study monitor during on-site monitoring visits.

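### The compliance formula counts every unreturned tablet as taken and does not match tablets to days, so subjects with unreturned bottles get wrong compliance values

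*SAP*

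**What the plan says.** The numerator of the ratio in SAP Section 3.6.4 is "the total number of tablets dispensed minus the total number of tablets returned". For the denominator and the scaling, the SAP has this difference "divided by two times the number of days during the treatment period, then multiplied by 100". Just before that sentence, the section introduces a separate quantity ("Days of possible exposure is defined as"): last dose date minus first dose date, plus 1. It also has a fallback: "When the last known dose date is missing, the last known clinic visit date during the treatment period will be used". In that case the 1 is not added. The two day counts have different names and the SAP does not link them. Protocol Section 10.7.4 has the same ratio without the missing-date rule.

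On supply, Protocol Section 6.2 states "Each bottle will contain sixty-six (66) tablets". SAP Section 2.2.1 provides one bottle at each of Visits 2, 4, 5, 6 and 7, then "two bottles of drug at Visit 8". Visit 3 is a clinic visit with no drug dispensed or collected (Protocol Section 8.2.2 and the schedule of assessments). Subjects are asked to bring unused drug back, but neither document says how a bottle that never returns enters the calculation.

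Compliance is summarised by arm and tabulated in bands with cut points at 80%, 100% and 120%.

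**The concern.** The numerator and denominator can cover different periods. If a subject disappears after a dispensing visit and no last dose date is known, the fallback ends the day count at that visit. The bottle handed over at that visit still counts as fully consumed. The subject whose intake is least well documented can then receive one of the highest compliance values.

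The undefined denominator is a second problem: two programmers could follow the text and produce results on opposite sides of 100% for the same subject. A third does not depend on dates at all: bottles not returned at the end of the study hide under-dosing.

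At stake is whether the planned compliance tables describe adherence in each arm, particularly if loss to follow-up or bottle return differs between arms.

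**Working it through.** **Inputs.** 66 tablets per bottle (Protocol 6.2). Two tablets per day, and one or two bottles per dispensing visit as above (SAP 2.2.1). Nominal visit days 15, 29, 57, 85, 113 and 141 for Visits 3 to 8. First dose on the evening of Day 1 (Protocol 6.3). Planned treatment of 26 × 7 = 182 days.

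**Sanity check.** The documents state no compliance figure to reproduce. For a perfect completer the formula works: 7 × 66 = 462 dispensed, 2 × 182 = 364 taken, 98 returned, and (462 − 98)/364 = 100.0%.

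**Dropping the plus 1 is not an error.** From the evening dose on Day 1 to the morning dose on Day 29 there are 1 + 27 × 2 + 1 = 56 doses, which equals 2 × 28.

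**Subject with a missing last dose date and an unreturned final supply.** Assume visits on nominal days and earlier leftovers returned. Let *d* = visit day − 1, *a* = fraction of doses taken up to the last visit, and *N* = tablets dispensed at that visit. Then

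- fallback denominator: (2*ad* + *N*)/(2*d*) = *a* + *N*/(2*d*)
- planned-length denominator: (2*ad* + *N*)/364

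At Visit 3 nothing has been counted, so the numerator is simply 66.

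| Last visit | *d* | *N* | Fallback days, *a* = 1 | Fallback days, *a* = 0.8 | 182 days, *a* = 1 |
|---|---|---|---|---|---|
| 3 | 14 | none | 66/28 = 235.7% | same | 66/364 = 18.1% |
| 4 | 28 | 66 | 122/56 = 217.9% | 110.8/56 = 197.9% | 122/364 = 33.5% |
| 5 | 56 | 66 | 178/112 = 158.9% | 155.6/112 = 138.9% | 178/364 = 48.9% |
| 6 | 84 | 66 | 234/168 = 139.3% | 200.4/168 = 119.3% | 234/364 = 64.3% |
| 7 | 112 | 66 | 290/224 = 129.5% | 245.2/224 = 109.5% | 290/364 = 79.7% |
| 8 | 140 | 132 | 412/280 = 147.1% | 356/280 = 127.1% | 412/364 = 113.2% |

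On fallback days at Visits 4 to 8, the excess over dosing up to the last visit is *N*/(2*d*), whatever the earlier dosing: 117.9, 58.9, 39.3, 29.5 and 47.1 points. At 60% prior dosing, loss after Visit 7 reads 60 + 29.5 = 89.5%. With the ±3-day visit windows and perfect dosing, the range over Visits 3 to 8 is 128.7% (Visit 7 on Day 116: 296/230) to 300% (Visit 3 on Day 12: 66/22).

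**Completer who does not return the two Visit 8 bottles.** With dosing at 182 days the denominator is 364 under both readings, and the numerator is 280*a* + 132. At *a* = 0.75, (210 + 132)/364 = 94.0%. At *a* = 0.60, (168 + 132)/364 = 82.4%. If the same dosing continued to the end, both subjects belong below 80% but are tabulated between 80% and 100%.

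**Zero days.** Loss straight after Visit 2 with a first dose dated Day 1 gives 66 tablets over 0 days.

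**The case against.** The strongest objection is that the fallback belongs to possible exposure, while the compliance sentence uses a different, undefined term. That is correct, so the inflated values cannot be presented as the only result of the text. It does not rescue the rule, because the 182-day reading is also wrong: a perfect doser lost after Visit 4 reads 33.5%.

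A reader might infer that everyone lost to follow-up will be reported well above 100%. The documents do not support that. The last dose date must be missing and the final supply must stay out. Early terminators are to have the Visit 9 procedures, which include drug return (Protocol Section 8.2.8), so withdrawals who attend are largely unaffected. The values above 120% at Visits 6 and 7 also depend on good dosing beforehand.

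A reader might also infer a general division by zero. That is an edge case: it needs no visit after Day 1 and a first dose dated Day 1. That dose is taken at dinner, after the visit, so it may never be confirmed, and the safety and ITT sets both require at least one dose.

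Finally, a reader might infer damage to the efficacy conclusions. No efficacy model uses compliance, and the per-protocol set is limited to subjects who complete as planned, so lost subjects are already outside it. Values above 120% have their own row and would be visible. The masked completer, at 94% or 82%, would not be.

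**Conclusion.** The point holds for the descriptive compliance summaries, and under either reading of the denominator. On possible-exposure days, the natural reading though not a stated one, affected subjects are overstated: 129.5% to 236% after perfect prior dosing on nominal visit days, and 109.5% to 198% across Visits 4 to 8 with 80% prior dosing. On 182 days most of the same subjects are understated, from 18% after Visit 3 to 80% after Visit 7. Separately, a completer at 75% who keeps the two Visit 8 bottles reads as 94% on both readings.

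The documents give no rate of missing dose dates or unreturned bottles, so the shift in an arm mean cannot be fixed. On the possible-exposure reading, each 1 in 100 subjects affected at Visits 4 to 8 raises the mean by between 29.5/100 = 0.3 and 117.9/100 = 1.2 points. The point should be corrected in the SAP, but it does not threaten the primary or key secondary analyses.

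**What to change.** In SAP Section 3.6.4:

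- Define the compliance denominator per subject, and state how it relates to possible exposure.
- Compute compliance from first dose to the last visit with a tablet count. Exclude tablets dispensed at or after that visit. With the first dose in the evening, the days are that visit date minus the first dose date.
- Remove any interval whose bottles were not returned from both numerator and denominator.
- Report subjects with no counted return as not evaluable. This also disposes of the zero-day case and of loss after Visit 3.
- Tabulate the number of subjects with unreturned bottles by arm.

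Under this rule a perfect doser reads 100% at each of Visits 4 to 8 (56/56, 112/112, 168/168, 224/224, 280/280), and the 75% completer reads 210/280 = 75%.

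The cost is SAP wording and programming. Protocol Section 11.8 already requires accountability records with dates, quantities and subject numbers, but the sponsor should confirm that counts can be linked to dispensing intervals in the analysis data. The drawback is that the summary omits unaccounted intervals and so describes subjects who return bottles, which is why the count by arm is needed beside it.
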